6.1.5.4 Proportion of children referred with hypoxaemia who receive oxygen at hospital

Children with hypoxaemia (according to country's specific cut-off) who received a referral advice at Day0 and oxygen at hospital (according to hospital records) will be counted in the numerator. All children recruited will be in the denominator.

Furthermore, children with hypoxaemia who were referred and children with hypoxaemia who were referred and admitted to hospital will be summarised using all children recruited as denominator.

Additionally, the proportions will be calculated and reported using only children with hypoxaemia as denominator.

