Additionally, visit information from government-designated hospital records will be collected retrospectively for children whose caregiver reported at Day 7 phone follow-up that they attended hospital, including clinical assessment on arrival (vital signs, admitting diagnosis), admission details (duration, if oxygen was administered, intensive care admission) and admission outcome (final diagnosis, discharge against medical advice, death). The same data will be collected for children who attended a non-hospital higher-level of care (emergency or admission unit of a primary or secondary care facility).

It is expected that some participants may present at the same or another health facility enrolled in the study during the follow-up period. These visits and the findings will be recorded on the appropriate scheduled / unscheduled visit eCRFs.

[figure not shown]
[figure not shown]
[figure not shown]

Fig. 5. Flowchart of the pre-post study. CDSA = Clinical Decision Support Algorithm. CG = Caregiver. HCP = Healthcare provider. OPD = Out-patient department.

Tab. 4. Schedule of the visits and associated CRFs for the pre-post study. The different types of staff collecting data are represented by the following icons:

Research assistant rotating
between different referral health
facilities

Call centre-based research assistant

		Health facility baseline visit		Higher level of care visit ^{1,2}		Follow-up or unscheduled visit at enrolled health facility		Phone follow-up
		Time point		Day 0		Day 0-7		Day 7 [7 - 10]
		Data collection method		Prospective data collection		Review of medical records		Phone interviews
		Study phase		Pre	Post ³			Pre
Events		Forms						Post ³
Informed consent				-				
Screening				TIMCI-01				
Identification & contact information	Full identification	TIMCI-02a						
	Contact information	TIMCI-02b						
	Identification and contact information check	TIMCI-02c						
	Referral facility identification	TIMCI-02d						
	Follow-up identification check	TIMCI-02e						
Socio-demographics		TIMCI-03						
Visit info	Care seeking behaviour, transport and costs for visiting health facility reported by caregiver	TIMCI-04a						
	Visit and admission info recorded by referral facility (medical records, registries) ²	TIMCI-04b						
	Patient journey reported by caregiver at follow-up	TIMCI-04c						
Clinical presentation & medical history	Clinical presentation and medical history reported by caregiver at baseline	TIMCI-05a						

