Data that will be collected at Day 7 follow-up will include cure status (recovery from illness as reported by the caregiver), hospitalisation and death between Day 0 and Day 7. If appropriate, name of the referral facility and duration of hospitalization will be collected to facilitate the retrospective data collection at referral hospital level.

Higher level of care visit

Data collection at this level of care will be conducted retrospectively. A quantitative research assistant using the EDC mobile application will collect data from referral facility records, registries and discharge summaries for children whose caregiver reported at Day 7 phone follow-up that they attended a government-designated referral facility between Day 0 and Day 7. This includes attendance to hospital or emergency / inpatient area of a larger primary or secondary care facility (e.g., study facilities that can admit paediatric patients). Personally identifiable information will be collected to cross-check the identity of the patients. Arrival date and time, basic clinical information on arrival and, if admitted, admission and discharge diagnosis and admission duration will be collected. If available, data on oxygen saturation at admission, oxygen administration and intensive care unit (ICU) admission and duration will also be recorded.

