7.2.4 Data quality assurance and control

Quality assurance activities across all studies will be more intense during study start-up to ensure quality data practices are instituted from the start of the trial. Further details will be given in the DMP and SOPs.

All research assistants will be trained to provide information and seek written consent using the information and consent form. Separate trainings will cover all aspects of quantitative data collection and all aspects of qualitative data collection. A competency assessment using scenarios will be done before commencing field work.

Data reconciliation between the different visits of the same child will be one of the most crucial data quality activities in the pre-post study. Specific procedures will be developed for this purpose. To identify repeat visits of children that may re-attend the study facility where they enrolled, or any other study facility during the follow-up period, participants will be given a study card (or sticker) with a unique ID number. Retrospective search for data at referral level will be restricted to facilities within the geographical area where the study is running and will be targeted to include only children reported to have attended hospital by the caregiver at follow-up and those lost to follow-up. The name of the referral facility will be requested during the follow-up call. If available, it should further restrict the scope of the search and the probability of negative matches when cross-checking the participant identity. Children who re-attend any study facility more than 28 days after their previous enrolment will be enrolled for the new disease episode and given a new ID number. If available, the old ID number will be recorded to facilitate linking of the different disease episodes. Data to be potentially reconciled will be flagged by automated cross-check of a set of personal identifiers. Given that personal identifiers may not be identically recorded at each visit, fuzzy matching methods will be used to calculate a score of similarity between records and likelihood that they relate to the same child. Reconciliation of records with high similarity scores will be manually validated.

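### Hospital oxygen is counted only from a usable hospital record, while children without one stay in the denominator, so each planned proportion is understated

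*SAP*

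**What the plan says.** SAP 6.1.5.4 defines the numerator as hypoxaemic children who "received a referral advice at Day0 and oxygen at hospital (according to hospital records) will be counted in the numerator". For the main version, "All children recruited will be in the denominator"; in addition, "the proportions will be calculated and reported using only children with hypoxaemia as denominator". The same section summarises hypoxaemic children who were referred, and those referred and admitted. It gives no rule for a child whose record was not sought, not found or silent on oxygen.

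The record source is described in three places in the Protocol:

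- Section 6.5.1: "visit information from government-designated hospital records will be collected retrospectively for children whose caregiver reported at Day 7 phone follow-up that they attended hospital". It adds: "The same data will be collected for children who attended a non-hospital higher-level of care". Whether oxygen was administered is listed among the admission details.
- Section 7.1.1: records are collected where the caregiver reported "that they attended a government-designated referral facility between Day 0 and Day 7". On content: "If available, data on oxygen saturation at admission, oxygen administration and intensive care unit (ICU) admission and duration will also be recorded".
- Section 7.2.4: "Retrospective search for data at referral level will be restricted to facilities within the geographical area where the study is running". This section extends the search to children lost to follow-up, whom 6.5.1 and 7.1.1 do not mention.

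Hospitalisation is defined from the Day 7 assessment (SAP 6.1.1), and that call asks about both government and private admissions (Protocol 6.5.1).

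**The concern.** The numerator requires positive evidence from a source that is incomplete by design, and neither denominator requires that the source was available. Oxygen given at a private hospital that is not government-designated, or at a hospital outside the study area, cannot enter the numerator. Nor can oxygen given to a child whose record could not be matched or did not mention it. All these children remain in the denominator.

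A reader will take this outcome as information on what happened to hypoxaemic children after referral. The planned referred-and-admitted summary will probably be set beside it. Because admission has wider coverage than oxygen, the gap between the two would mix children who truly received no oxygen with children whose oxygen status was never seen. Incomplete record retrieval could then be reported as a shortfall in hospital care.

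**Working it through.** The plan states no expected rate, precision or retrieval rate for this outcome, so there is no figure to reproduce. The check is of the definition, followed by its arithmetic.

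**Step 1. Coverage of the two sources**

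| | Admission | Oxygen |
|---|---|---|
| Source | Caregiver at Day 7 | Hospital record |
| Facilities | Government or private | Government-designated, plus non-hospital higher-level care |
| Area | No limit stated | Study area |
| Further conditions | Day 7 contact made | Identity matched; oxygen noted |

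Oxygen is not among the Day 7 caregiver items listed in Protocol 7.1.1, so the caregiver report offers no fallback.

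**Step 2. Effect on the planned proportions**

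Let X be the number of hypoxaemic children who were referred and truly received oxygen at hospital. Let N be the denominator (all recruited, or all hypoxaemic). Let u be the share of X whose record was sought, matched and shows oxygen.

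- True proportion = X / N
- Proportion under SAP 6.1.5.4 = uX / N
- Ratio = u, so relative understatement = 1 - u

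N cancels, so the relative understatement is the same for both planned denominators.

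**Step 3. Size**

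The documents give no value for u. Assume that 50-80% of children have a usable record and that usability is unrelated to oxygen receipt, so that this rate can stand for u:

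- u = 0.80: 1 - 0.80 = 20% understatement
- u = 0.50: 1 - 0.50 = 50% understatement

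**Step 4. Illustration on a planned denominator (all inputs assumed)**

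Suppose 60% of referred hypoxaemic children receive oxygen, 70% have a located record, and 90% of located records note oxygen when it was given. Then u = 0.70 x 0.90 = 0.63. With all hypoxaemic children as denominator:

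| Share referred | True | Under the SAP rule |
|---|---|---|
| 50% | 0.60 x 0.50 = 30.0% | 30.0% x 0.63 = 18.9% |
| 70% | 0.60 x 0.70 = 42.0% | 42.0% x 0.63 = 26.5% |
| 90% | 0.60 x 0.90 = 54.0% | 54.0% x 0.63 = 34.0% |

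The relative understatement is 1 - 0.63 = 37% in each row.

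**Step 5. Behaviour of the proposed report (same assumptions)**

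Take 100 referred hypoxaemic children who attended hospital, of whom 60 received oxygen, with oxygen status usable for 63% of recipients and of non-recipients alike.

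- (a) oxygen recorded as given: 60 x 0.63 = 37.8
- (b) oxygen recorded as not given: 40 x 0.63 = 25.2
- (c) not ascertained: 100 - 63 = 37
- (a)/(a+b) = 37.8 / 63 = 60.0%
- Bounds: 37.8% if all of (c) had no oxygen; (37.8 + 37)/100 = 74.8% if all did

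If records silent on oxygen were placed in (b), the 70 located records would give 37.8 / 70 = 54.0%, still below the true 60%. Silent records therefore belong in (c).

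**The case against.** The strongest reply has four parts.

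- **The outcome is minor.** It is listed among the other outcomes of interest, is reported post-intervention only, and has no pre-post contrast. This stands and limits the consequence.
- **Retrieval is better organised than a bare reading suggests.** Protocol 7.2.4 uses the facility name given by the caregiver, fuzzy matching and manual validation, and includes children lost to follow-up. Protocol 6.5.1 covers non-hospital higher-level care and lists oxygen administration without the availability qualifier. These steps raise u. They do not bring in hospitals outside the search, and 7.1.1 still accepts that oxygen may be unavailable.
- **The SAP never says that missing means no oxygen.** True: elsewhere it states its assumption for absent data (6.1.2.1, 6.1.2.5, 6.1.2.7), and here it does not. The coding is nevertheless fixed by the numerator and denominators, so the definition followed exactly gives the biased figure.
- **Other planned reporting exposes the gap.** The referred-and-admitted summary does so in part, but it does not count located records and has wider coverage. SAP 6.3 sets an imputation rule only for secondary outcomes that rely on Day 7 data. It also plans to describe missing data without naming hospital records.

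Two stronger readings are tempting. A reader might infer that a true 80% would be published as 40-64% (0.80 x 0.50 to 0.80 x 0.80). That needs referred hypoxaemic children as the denominator, which the SAP does not plan. The planned figures also carry referral and attendance, so only the relative factor transfers. A reader might also infer that the Kenya-Senegal comparison is distorted. That would require retrieval to differ between countries, and nothing in the documents shows that it does.

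**Conclusion.** The point holds. As defined, each proportion in SAP 6.1.5.4 is understated by the share of oxygen recipients without a usable record. That follows from the definitions alone and holds for any retrieval below 100%. The 20-50% size rests on two assumptions that the documents neither support nor contradict: 50-80% of records usable, and usability unrelated to receipt. The documents do not support an absolute size, a direction of bias between countries, or any effect on primary or secondary results. The defect is confined to one descriptive post-intervention outcome, but that outcome would be misread if published as defined.

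**What to change.** In SAP 6.1.5.4, take referred hypoxaemic children who were reported to have attended hospital or were found in hospital records, and report by country:

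- (a) oxygen recorded as given;
- (b) record located and oxygen recorded as not given;
- (c) not ascertained: private or out-of-area facility, no matched record, or record silent on oxygen.

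Give (a)/(a+b) alongside the planned proportions. Add a lower bound counting all of (c) as no oxygen and an upper bound counting all of (c) as oxygen. The bounds are needed because children with usable records may not be representative. They matter most if records seldom state that oxygen was withheld, since (b) would then be too small and (a)/(a+b) too high.

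Reconcile Protocol 6.5.1 and 7.1.1 with 7.2.4 on whether records are searched for children lost to follow-up.

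The cost is SAP wording and an extra table column. The added proportion has a smaller denominator and a wider interval. One point to confirm first is whether the referral-facility form separates oxygen not given from oxygen not documented; the form is not reproduced in the documents. If it does not, (b) and (c) cannot be fully separated, and the table should say so.

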Other outcomes of interest – hypoxaemia

- ξ Proportion of children with severe ($\text{SpO}_2 < 90\%$), moderate ($\text{SpO}_2 90 – 91\%$) and mild hypoxaemia ($\text{SpO}_2 92 – 93\%$), adjusted for sites at high altitude
- ξ Proportion of children with hypoxaemia (according to differing cut-offs) with severe complication
- ξ Proportion of children with severe hypoxaemia not meeting any other clinical criteria for severe disease
- ξ Proportion of children referred with hypoxaemia who receive oxygen at hospital

Other outcomes of interest – referral and follow-up

- ξ Proportion of children with non-severe disease referred to a higher level of care on Day 0
- ξ Average length of stay (in days) of children admitted to hospital
- ξ Proportion of children attending scheduled follow-up at the same facility by Day 7
- ξ Proportion of children presenting for unscheduled follow-up to any health facility by Day 7

Other outcomes of interest – antimicrobial prescription

- ξ Proportion of children prescribed a diagnosis-appropriate antibiotic
- ξ Proportion of febrile children tested for malaria at Day 0
- ξ Proportion of malaria positive children prescribed an antimalarial
- ξ Proportion of malaria negative children prescribed an antimalarial
- ξ Proportion of untested children prescribed an antimalarial

Other exploratory analyses:

- ξ Additional sociodemographic characteristics: urban / rural location, distance from health facility, key household indicators such as maternal age and education
- ξ Additional complaint / symptom categories (fever, diarrhoea and other) and time since onset of symptoms
- ξ Alternative hypoxaemia cut-offs
- ξ Healthcare provider severity classification
- ξ Facility and health system factors – type of facility, healthcare provider qualification and previous training

- ξ Time point (pre, early, late) and pilot site data

6.4.2 **Other mixed methods studies**

These studies will mostly be exploratory, particularly the qualitative studies, which seek to understand perceptions, values, attitudes and beliefs. Process evaluation criteria will be evaluated according to the MRC criteria.³⁵

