6.6.1 Quasi-experimental pre-post study

The sample size for the quasi-experimental pre-post study is calculated separately for each country, based on comparison between pre- and post-intervention periods.. The following assumptions are used:

- ξ power 80%
- ξ alpha 0.05
- ξ pre-intervention referral to a higher level of care 3% (based on informal estimates from country research teams and SPA data from various countries), with a minimum detectable difference of 50%
 - We have chosen a large detectable difference for referral from primary care as not all children referred will complete referral, i.e. a 50% increase in referral rate may only result in a 20 – 30% total increase in completed referrals (this will be assessed as a secondary outcome and is therefore not a component of the sample size calculation)
- ξ pre-intervention antibiotic prescription of 60% (based on informal estimates from countries, SPA data and other observational studies)
- ξ intra-cluster correlation coefficient (ICC) of 0.005 for referral and 0.05 for antimicrobial prescription

- ξ Kenya – estimated average cluster size of 230 children / month (assuming a cluster ratio of health centres : dispensaries 1:2, with 100 / month in dispensaries and 500 / month in health centres)
- ξ Senegal – estimated cluster size of 170 children per month (based on DHIS2 data on outpatient consultations in Thies in 2019)

For the referral primary outcome, we therefore initially estimated requiring the following sample size:

- ξ Kenya – 17 facilities, recruiting an average of 690 children per facility in each period, equating to 11,730 children per period
- ξ Senegal – 18 facilities, recruiting an average of 510 children per facility in each period, equating to 9,180 children per period

For the antibiotic prescription primary outcome, this would enable a minimum detectable reduction of 18% in Kenya and Senegal.

Following lower than anticipated recruitment in the pre-intervention period, sample size calculation was revised. As a result, two additional facilities were added per country and the pre-intervention period was extended from an initially anticipated 3 months to a 6 – 8 month period. A decision was also taken to target a post-intervention sample size of at least the same as the pre-intervention sample size, as well as a minimum duration of 9 months post-intervention to allow for stabilisation over time and some seasonal overlap of pre- and post-intervention periods.

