6.1.2 Health, hospitalisation and referral outcomes

6.1.2.1 Proportion of children with a severe complication by Day 7

Severe complication is defined as death or secondary hospitalisation. Secondary hospitalisation refers to any delayed hospitalisation (occurring at any point greater than 24hrs after the Day 0 consultation) and any hospitalisation occurring without a referral. Information on death and hospitalisation will be taken from Day7 follow-up assessment.

Death will be counted in the numerator if death date is within 7 days of Day0 (7th day included). Hospitalisation will be counted in the numerator if the child was not referred at Day0 or hospital admission date is within 7 days of Day0 (7th day included) but after 24hrs of Day0.

The denominator will be all children recruited. Children for whom no death and hospitalisation data are available or withdrew prematurely from the study will be assumed to be alive and not hospitalised by Day7.

6.1.2.2 Proportion of children admitted to hospital within 24 hours of Day 0 consultation and as a result of a referral

Information on hospitalisation will be taken from Day7 follow-up assessment.

Hospitalisation will be counted in the numerator only if the child received a referral advice (as per definition above) at Day0 and hospital admission date is within the end of the following day. The denominator will be all children recruited.

Additionally, the proportion will be calculated and reported using only children who were referred as denominator.

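### SAP 6.1.5.4 does not plan the proportion it names: oxygen receipt is never divided by referred hypoxaemic children

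*SAP*

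**What the plan says.** Protocol 6.4.1 lists, among the other outcomes of interest for hypoxaemia: "Proportion of children referred with hypoxaemia who receive oxygen at hospital". SAP 3.1.4 repeats the same wording and places it under outcomes assessed after the intervention only. SAP 6.1.5.4 keeps it as its title.

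The definition in SAP 6.1.5.4 then runs as follows:

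- Numerator: children with hypoxaemia "who received a referral advice at Day0 and oxygen at hospital (according to hospital records) will be counted in the numerator".
- First denominator: "All children recruited will be in the denominator".
- Supporting summaries, both divided by everyone recruited: "children with hypoxaemia who were referred and children with hypoxaemia who were referred and admitted to hospital will be summarised using all children recruited as" […].
- Second denominator: "Additionally, the proportions will be calculated and reported using only children with hypoxaemia as denominator".

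Elsewhere the SAP does add a conditional denominator. For admission within 24 hours after referral (6.1.2.2) and for completed referral (6.1.2.5) it says: "Additionally, the proportion will be calculated and reported using only children who were referred as denominator". For scheduled and unscheduled follow-up (6.1.6) it adds the children for whom follow-up advice was, or was not, recorded.

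**The concern.** As named, the outcome has a population (children referred with hypoxaemia) and an event (oxygen at hospital). It asks what happens after the referral decision. Neither planned denominator is that population. Division by all recruited children brings in how common hypoxaemia is, whether SpO2 was recorded, and whether the child was referred. Division by all hypoxaemic children removes prevalence but keeps the referral decision.

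A low hypoxaemic-only figure could therefore mean that few hypoxaemic children were referred, or that few of those referred received oxygen. These are different problems, at different levels of the health system. Protocol 6.1.2 describes oxygen at Senegal's referral health centres as mostly available but little used, so receipt after referral is a real question for this study.

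**Working it through.** The documents give no expected value, sample size or precision for this outcome, so there is no plan figure to reproduce. The check is of which ratios the text produces.

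**Notation, from SAP 6.1.5.4.** N = all recruited; H = hypoxaemic; R = hypoxaemic and referred at Day 0; A = hypoxaemic, referred and admitted; O = hypoxaemic, referred and given oxygen.

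**Planned outputs.** O/N, R/N and A/N, then O/H, R/H and A/H. The named outcome is O/R. R appears only as a numerator.

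**Could the second denominator mean the referred subset?** No. The paragraph just before it names hypoxaemic children who were referred as a separate group, so the unqualified term covers all hypoxaemic children.

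**What O/H measures.** O/H = (R/H) × (O/R), so O/R = (O/H) ÷ (R/H). Hold O/H at an assumed 27%:

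| Assumed share referred, R/H | O/R |
|---|---|
| 30% | 0.27 ÷ 0.30 = 90% |
| 60% | 0.27 ÷ 0.60 = 45% |
| 90% | 0.27 ÷ 0.90 = 30% |

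**How far the planned figures move when O/R does not.** Take N = 11,730, the initially planned size for Kenya (Protocol 6.6.1, "equating to 11,730 children per period"). Assume 1% hypoxaemia and O/R = 50%, neither of which is in the documents. Then H = 0.01 × 11,730 ≈ 117.

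| R/H | R | O | O/N | O/H | O/R |
|---|---|---|---|---|---|
| 30% | 35 | 18 | 0.15% | 15% | 50% |
| 60% | 70 | 35 | 0.30% | 30% | 50% |
| 90% | 106 | 53 | 0.45% | 45% | 50% |

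Counts are rounded; the percentages use unrounded values. If hypoxaemia ranges over 0.5% to 3%, O/N runs from 0.005 × 0.30 × 0.50 = 0.075% to 0.03 × 0.90 × 0.50 = 1.35%. O/H and O/R do not change with prevalence.

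**Measurement also enters O/N.** SAP 6.1.1 treats a child without an SpO2 value as normoxaemic. SAP 4.2 says oximetry was indicated for all children in Kenya but for a subset in Senegal. O/N can therefore differ between the countries for reasons unrelated to oxygen.

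**Can a reader recover O/R?** Yes: (O/N) ÷ (R/N) = (O/H) ÷ (R/H) = O/R exactly, because O is a subset of R. SAP 6.2.1 plans counts as well as percentages. In the middle row above, 35 of 70 is 50%, with an exact binomial 95% interval of 37.8% to 62.2%. That interval ignores facility clustering. The SAP does not ask for the ratio or for an interval on it.

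**The case against.** The strongest reply is that nothing is lost. O and R are both reported as counts, so the named proportion is one division away, and a binomial interval follows. That stands. A reader might infer that only a rough estimate without an interval could be had; the planned counts do not support that. Only an interval that allows for facility clustering would need the individual data.

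Second, a reader might infer that the hypoxaemic-only denominator is invalid. It is not. All hypoxaemic children are a legitimate denominator for the care pathway, since an unreferred hypoxaemic child counts as a failure of that pathway. For 24-hour admission, Protocol 6.4.1 prefers all enrolled children because a proportion among the referred could look high while too few are referred. Similar reasoning could support O/N and O/H here, but the documents do not give it for this outcome. Even for 24-hour admission the SAP adds the referred-only figure. The argument supports keeping the existing denominators; it does not support leaving out the one in the title.

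Third, O/R does not isolate oxygen access. Oxygen data come from hospital records. Protocol 6.5.1 and 7.1.1 seek these at government-designated facilities for children reported at Day 7 to have attended, and Protocol 7.2.4 extends the search to those lost to follow-up. O/R therefore still includes referral completion, use of private hospitals and record retrieval. This stands, and it is why a second denominator and a stated limitation are needed.

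Finally, SAP 4.1 promises confidence intervals for primary and secondary outcomes. Their absence here follows from the outcome's rank and its lack of a pre-intervention comparison, not from the choice of denominator.

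**Conclusion.** The point holds as a mismatch between a listed outcome and its definition. The protocol and SAP name oxygen receipt among referred hypoxaemic children. SAP 6.1.5.4 plans two other proportions under that title, and no other section supplies the named one. It also departs from the SAP's own practice in 6.1.2.2, 6.1.2.5 and 6.1.6.

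Its reach is limited to the reporting of one descriptive, post-intervention outcome. It has no bearing on the primary or secondary analyses, and the estimate can be derived from planned counts. The factorisation of O/H into referral and oxygen receipt is exact. The sizes shown (27% with 30% to 90% referred; 0.5% to 3% hypoxaemia; 50% oxygen receipt) are assumptions that show how far the figures can diverge, not predictions for this study.

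**What to change.** In SAP 6.1.5.4:

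1. Make hypoxaemic children referred at Day 0 the denominator for the named outcome, with a 95% confidence interval.
2. Add a second denominator of referred hypoxaemic children with a located hospital record (or admitted), also with a 95% confidence interval. State whether the intervals allow for facility clustering.
3. Keep all recruited children and all hypoxaemic children as denominators, labelled as pathway summaries.
4. State that oxygen data come from hospital records, so the referred-only figure still reflects referral completion and record retrieval.

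The cost is two further denominators on data already collected. Data collection, sample size and the primary analysis do not change.
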